# **3** STATISTICAL METHODS

## 3.1 General Considerations

All statistical calculations will be primarily performed using SAS® System Version 9.4 or higher. Categorical data will be summarized by the frequency counts and percentage of participants in each category. Continuous variables will be summarized by descriptive statistics, including number of observations, mean, standard deviation, median, first quartile, third quartile, minimum, and maximum.

## **3.1.1 Definition of Baseline**

Unless otherwise specified, baseline will be defined as the last non-missing valid observation prior to the first administration of investigational product (IP). In cases where baseline measurements are taken on the same day as IP and no times are reported, it will be assumed that these measurements are taken prior to IP being administered.

## 3.1.2 Analysis Windows

Analysis visit windows will be used for all visit-based assessments to map longitudinal observations to scheduled visits and thereby allow for by-visit analyses, since not all assessments are performed on the scheduled day. Unless otherwise specified, all longitudinal efficacy, safety, and biomarker data analyses will be based on the analysis visit windows. The analysis visit windows will be calculated by bisecting the interval between adjacent scheduled visit days except for the first post-treatment visit. The first post-treatment visit will start at Day 2. The detailed analysis visit windows will be specified in the statistical programming plan (SPP).

The actual assessment day will be mapped to the windows defined for each scheduled study visit with following rules:

- If more than one assessment falls within a visit window, the closest non-missing assessment to the scheduled day will be used in the analysis.
- If 2 non-missing assessment actual dates are equidistant from the target day, the later visit will be used in the analysis.
- For retest value of laboratory data, the retest value will be chosen.

All observations will be included in data listings.

## **3.2 Protocol Deviations**

All protocol deviations will be classified as critical protocol deviations, major protocol deviations, or minor protocol deviations. A critical protocol deviation is a significant departure from protocol requirements resulting in a life-threatening risk to an individual subject, or where the safety or well-being of trial subjects has been or has significant potential to be jeopardized, a significant portion of the clinical trial data might be unreliable, and/or a significant portion of critical data being jeopardized. All the protocol deviations will be listed, and the critical protocol deviation will be summarized. Some classifications of critical protocol deviations are listed below.

- Did not meet inclusion criteria or met exclusion criteria
- Blinding of treatment assignment was broken by site investigator
- Received prohibited concomitant medication
- Serious breach of good clinical practice.

The list may be updated and will be finalized and documented prior to the database lock for the interim analysis.

### 3.3 Analysis Sets

### 3.3.1 All participant analysis set

This analysis set includes all participants screened for the study and will be used for the reporting of participant disposition.

## 3.3.2 Full analysis set

The full analysis set includes all randomized participants who receive any dose of IP. Participants will be analyzed according to the treatment randomized. The efficacy analysis will be based on the full analysis set.

### 3.3.3 Safety analysis set

The safety analysis set includes all participants who receive any dose of IP. Participants will be analyzed according to the treatment that they received. The safety, pharmacodynamics (PD), analyses will be based on the safety analysis set.

### **3.3.4** Pharmacokinetic analysis set

The pharmacokinetic (PK) analysis set includes all participants who receive any dose of VIB7734 in the study and have at least 1 quantifiable serum PK observation post-first dose. Participants will be analyzed according to the treatment that they received. The PK analysis will be based on the PK analysis set.

#### **3.4** Study Participants

#### 3.4.1 Participant Disposition

A summary of participant disposition will be presented using the categories presented below.

- Screened
- Screen failed with reasons
- Randomized
- Randomized but not treated
- Randomized and treated
- Completed treatment
- Discontinued treatment with reasons
- Completed study
- Discontinued study with reasons

#### 3.4.2 Demographics, Baseline Characteristics, and Medical History

The demographics (age, gender, race, ethnicity, height, weight, and body mass index) will be summarized by treatment group and overall, for the full analysis set.

A summary of baseline characteristics, by treatment group and overall, for the full analysis set will include the following:

- Time from initial diagnosis to randomization
- SLE Disease Activity Index-2000 (SLEDAI-2K) total score
- SLEDAI-2K total score category ( $<10 \text{ vs} \ge 10$ )
- British Isles Lupus Assessment Group (BILAG)-2004 total score
- BILAG-2004 organ system involvement at baseline (yes vs no for each organ system domain). Involvement requires a baseline BILAG-2004 scale of A or B
- Physician global assessment (PGA) score
- Cutaneous Lupus Erythematosus Disease Area and Severity Index (CLASI) activity (CLASI-A)
- CLASI-A score category ( $<10 \text{ vs} \ge 10$ )

- Low C3 (below lower limit of normal (<LLN) (yes vs no)
- Low C4 (<LLN) (yes vs no)
- Positive rheumatoid factor (RF) (yes vs no)
- Region (Europe, North America, Latin America, and Asia)

American College of Rheumatology criteria will be summarized by treatment group and overall for the full analysis set. Significant medical history findings will be summarized by Medical Dictionary for Regulatory Activities (MedDRA) system organ class (SOC) and preferred term (PT) by treatment group and overall for the full analysis set.

#### **3.5** Investigational Product Exposure

The number of doses received, amount (mg) of the IP received, durations of the IP exposure, and total participant years exposure will be summarized by treatment using the full analysis set. The number and percentage of participants treated  $\geq 4$  weeks,  $\geq 12$  weeks,  $\geq 24$  weeks,  $\geq 36$  weeks, and  $\geq 48$  weeks will also be provided.

- Duration of the IP exposure is defined as (last dose date + 28 -first dose date + 1)
- The amount of IP received: if a participant received partial dose at a dosing visit, then the amount of IP at that dosing visit will be estimated based on the actual volume administered. The amount of VIB7734 is 0 mg for dosing visits with placebo administered.

Daxdilimab (HZN-7734) VIB7734.P2.S1 Statistical Analysis Plan

• Treatment compliance for an individual patient = (Total number of doses received)/ (Total number of doses planned per protocol) ×100%.

Furthermore, the time to discontinuation of IP will be presented as Kaplan-Meier plot including the number of participants at risk.

### **3.6 Prior and Concomitant Medications**

Number (%) of participants who receive prior medications and concomitant medications will be summarized by world health organization drug dictionary Anatomical Therapeutic Chemical category and PT based on the full analysis set and safety analysis set respectively. At each level of summarization, a participant is counted once if he/she reported one or more medications at that level. The concomitant medications will be summarized by category (immunomodulatory vs non- immunomodulatory medications). The prior and concomitant medications are defined as below.

[figure not shown]
- Prior medications are defined as medications with a stop date occurring before the first IP administration date.
- Concomitant medications are defined as medications with a stop date on or after the first IP administration date.

SLE disease related immunosuppressants including glucocorticoid (GC) at Baseline are defined as all immunosuppressants with an intake at the date of first dose of IP (ie, start date on or before the date of first dose and end date on or after date of first dose or ongoing). Disease related immunosuppressants at Baseline will be summarized in the following categories for the full analysis set.

- Baseline oral glucocorticoid (OGC) dose (≥10 mg/day vs. <10 mg/day of prednisone or equivalent)
- Baseline OGC use (yes vs no)
- Baseline OGC dose of prednisone or equivalent for participants on OGC at Baseline
- Baseline antimalarial use (yes vs no)
- Other immunosuppressants (mycophenolate, methotrexate, azathioprine, etc.) use at Baseline (yes vs no)
- OGC only
- Antimalarials only
- Other immunosuppressants only
- OGC and antimalarials only
- OGC and other immunosuppressants only
- Antimalarials and other immunosuppressants only
- OGC, antimalarials, and other immunosuppressants

Daxdilimab (HZN-7734) VIB7734.P2.S1 Statistical Analysis Plan

The number and percentage of participants who receive restricted medications beyond the protocol-allowed threshold during treatment period will also be summarized in the following categories for the full analysis set.

The selection of GC and non-GC immunosuppressants will be specified in the SPP. The missing start/stop date of medications will be imputed as appropriate, and the details of the imputation will be included in the SPP.

#### 3.7 Efficacy Analyses

#### **3.7.1 Primary Endpoint and Analyses**

#### 3.7.1.1 Primary endpoint and estimand

The estimand of primary interest is defined as follows, using composite variable strategy to address intercurrent events.

- Population: Participants in the full analysis set with active SLE despite receiving 1 or more standard of care treatments as defined by the inclusion-exclusion criteria of the study (excluding subjects from Russia and Ukraine sites)
- Variable (endpoint): Response in BICLA + OGC ≤ 7.5 mg/day and ≤ Day 1 dose at Week 48, where BICLA is defined by meeting the following criteria compared to Baseline:
  - BILAG-2004 Index improvement (all Baseline BILAG A improving to B/C/D, all Baseline BILAG B to C/D, and ≤ 1 new BILAG B and no new BILAG A).
  - No deterioration in SLEDAI-2K total score, where deterioration is defined as an increase from baseline of > 0 points in SLEDAI-2K.
  - No significant worsening in PGA score (< 0.3 point increase).

  - No use of restricted medications beyond the protocol-allowed threshold (see section 3.6) before assessment.
  - No discontinuation of IP.
- Intercurrent event:
  - Rescue medications: Captured in the primary variable definition.
  - Treatment discontinuation: Captured in the primary variable definition.
- Population-level summary: Difference in proportions of responders between the VIB7734 group and placebo group.

#### 3.7.1.2 Primary efficacy analysis

Participants with no BILAG A or B at baseline and no worsening in any organ systems ( $\leq 1$  new BILAG B and no new BILAG A), as well as participants with a baseline PGA score > 2.7 will be considered as having met the criteria for BILAG and PGA, respectively.

The proportion of participants achieving BICLA response + OGC  $\leq$  7.5 mg/day and  $\leq$  Day 1 dose prednisone or equivalent at Week 48 in the VIB7734 treatment group will be compared to that of the placebo group for the full analysis set using a logistic regression model with treatment, and randomization stratification factors included in the model.

The difference in proportions of responders between each of VIB7734 groups and placebo group will be estimated together with its associated 2-sided 90% confidence interval (CI) and p-value. The significance of treatment effect will be tested by using a 2-sided test at significance level  $\alpha$  of 0.1. Additionally, estimates of the response rate for each treatment group will be obtained, together with the associated standard error (SE).

Longitudinal presentations of results over time based on the same analysis will be created.

3.7.1.3 Supplementary analysis of primary endpoint

A supplementary analysis with the same model as primary analysis will be performed using a treatment policy strategy to address intercurrent events defined in section 3.7.1.1. All observed values will be used regardless of occurrence of an intercurrent event.

## 3.7.1.4 Handling plan for missing data

Intermittent missing data will be imputed using last observation carried forward approach (LOCF). Participants with missing primary outcome measures due to early discontinuation of study will be considered nonresponders. If any of the criteria cannot be evaluated at a visit, that criterion will be imputed using LOCF.

Missing items in SLEDAI-2K and BILAG-2004 will be imputed according to the specific rules described in Section 3.7.4.

## 3.7.1.5 Multiplicity adjustment

No multiplicity adjustment is planned since this is a phase 2 exploratory trial.

## 3.7.2 Secondary Efficacy Endpoints and Analyses

3.7.2.1 Secondary efficacy endpoints and estimands

The estimands are defined as follows, using composite variable strategy to address intercurrent events.

- Population:
  - CLASI: Participants in the full analysis set with active SLE and CLASI-A score
     ≥ 10 at Baseline despite receiving one or more standard of care treatments as
     defined by the inclusion-exclusion criteria of the study (excluding subjects from
     Russia and Ukraine sites).
  - OGC reduction: Participants in the full analysis set with active SLE taking an OGC of ≥ 10 mg/day of prednisone or equivalent at Baseline despite receiving one or more standard of care treatments as defined by the inclusion-exclusion criteria of the study (excluding subjects from Russia and Ukraine sites).
  - SRI-4 + OGC ≤ 7.5 mg/day and ≤ Baseline (Day 1) dose and LLDAS: Participants in the full analysis set with active SLE despite receiving one or more standard of care treatments as defined by the inclusion-exclusion criteria of the study (excluding subjects from Russia and Ukraine sites).
- Variable (endpoint):

- CLASI: ≥ 50% reduction in CLASI-A score at Week 12 defined by meeting the following criteria:
  - $\circ$  A  $\geq$  50% reduction of CLASI-A score at Week 12 as compared to Baseline.
  - No use of restricted medications beyond the protocol-allowed threshold (see section 3.6) before assessment.
  - No discontinuation of IP before assessment.
- SRI-4 + OGC ≤ 7.5 mg/day and ≤ Baseline (Day 1) dose: Response in SRI-4 + OGC ≤ 7.5 mg/day and ≤ Baseline (Day 1) dose at Week 48, where SRI-4 is defined by meeting the following criteria compared to Baseline:
  - Reduction from Baseline of  $\geq$  4 points in the SLEDAI-2K.
  - No new organ system affected as defined by one or more BILAG A or 2 or more BILAG B items.
  - $\circ$  No significant worsening in PGA score (< 0.3 point increase).
  - No use of restricted medications beyond the protocol-allowed threshold (see section 3.6) before assessment.
  - No discontinuation of IP.
- OGC reduction: Maintained OGC reduction from Week 36 to Week 48 defined by meeting the following criteria:
  - An OGC dose of  $\leq$  7.5 mg/day prednisone or equivalent at Week 36 that is maintained through Week 48.
  - No use of restricted medications beyond the protocol-allowed threshold (see section 3.6) before assessment.
  - No discontinuation of IP before assessment.
- LLDAS: Response in LLDAS at Week 48, where LLDAS is defined by meeting the following criteria:
  - A SLEDAI-2K  $\leq$  4, with no activity in major organ systems (renal, central nervous system (CNS), cardiopulmonary, vasculitis, fever) and no hemolytic anemia or gastrointestinal activity.
    - SLEDAI-2K organ system is define in section 3.7.3.1.8. Hemolytic anemia and gastrointestinal activity will be assessed by BILAG-2004 (present evidence of active hemolysis and gastrointestinal manifestation respectively).
  - No new lupus disease activity compared with the previous assessment measured by SLEDAI-2K.
    - New lupus disease activity is defined as present activity (item score >0) in at least one new SLEDAI-2K item compared with the previous visit.
  - A PGA  $\leq 1$  (on a scale of 0 to 3).
  - Current prednisone or equivalent dose of  $\leq$  7.5 mg/day.
  - Well-tolerated standard maintenance doses of immunosuppressive drugs and approved medications as allowed and specified in the protocol.

- Any discontinuation of permitted non-GC immunosuppressants is assumed to be due to toxicity.
- No use of restricted medications beyond the protocol-allowed threshold (see section 3.6) before assessment.
- No discontinuation of IP.
- Intercurrent event:
  - Rescue medications: Captured in the variable definition.
  - Treatment discontinuation: Captured in the variable definition.
- Population-level summary for all secondary endpoints: Difference in proportions of responders between VIB7734 and placebo.

3.7.2.2 Secondary efficacy analysis

SRI-4 + OGC  $\leq$  7.5 mg/day and  $\leq$  Baseline (Day 1) dose at Week 48 and LLDAS at Week 48 will be analyzed using the same logistic regression model as described in section 3.7.1.2 for the primary endpoint based on the full analysis set.

Maintained OGC reduction from Week 36 to Week 48 will be analyzed using a similar logistic regression model as described in section 3.7.1.2 replacing baseline OGC category ( $\geq 10 \text{ or } < 10 \text{ mg/day}$ ) with Baseline OGC dose based on subgroup of participants with OGC of  $\geq 10 \text{ mg/day}$  of prednisone or equivalent at Baseline.

Achieving a  $\geq$  50% reduction in CLASI-A score at Week 12 will be analyzed using a similar logistic regression model as described in section 3.7.1.2 including Baseline CLASI-A score as an additional covariate based on subgroup of participants with CLASI-A score  $\geq$  10 at Baseline.

The difference in proportions of responders of VIB7734 versus placebo will be estimated for all secondary endpoints together with its associated 2-sided 90% CI and p-value. In addition, estimates of the response rate for each treatment group will be obtained, together with the associated SE.

Longitudinal presentations of results over time based on the same analysis will be created.

3.7.2.3 Supplementary analysis of secondary endpoints

A supplementary analysis with the same model as described in section 3.7.2.2 for each secondary endpoint will be performed using a treatment policy strategy to address intercurrent events defined in section 3.7.2.1. All observed values will be used regardless of occurrence of an intercurrent event.

## 3.7.2.4 Handling plan for missing data

[figure not shown]
The missing data will be handled the same way as that for the primary endpoint analysis (see section 3.7.1.4).

## **3.7.3 Exploratory Efficacy Endpoints and Analyses**

## 3.7.3.1 Exploratory efficacy endpoints

[figure not shown]
CONFIDENTIAL AND PROPRIETARY

[figure not shown]

[figure not shown]

[figure not shown]

[figure not shown]

[figure not shown]

[figure not shown]

3.7.3.2 Exploratory efficacy analyses

[figure not shown]

## 3.7.4 Handling Missing Items of Clinical Outcome Assessments

The BILAG-2004, SLEDAI-2K, CLASI, **Sector** are clinician reported outcomes and will be captured electronically. There will be very few missing items expected. All PROs will be administered electronically too. Questions are mandatory so there will be very few missing items expected. But in case there are missing items, the following algorithms will be used to handle the missing items.

### 3.7.5 Subgroup Analysis

To explore the uniformity of the detected overall treatment effect, subgroup analyses on the primary endpoint and secondary endpoints of SRI-4 + OGC  $\leq$  7.5 mg/day and  $\leq$  Baseline dose and LLDAS will be performed for the following factors:

- SLEDAI-2K total score at screening (<10 points versus  $\geq$ 10 points)
- OGC dose at baseline (<10 mg/day versus  $\geq$ 10 mg/day prednisone or equivalent)
- Age (<55 versus  $\geq$ 55 years)
- Onset of disease (adult versus pediatric onset)
- BMI ( $\leq 30$  versus > 30 kg/m^2)
- Race (white, black or African American, other)
- Ethnicity (Hispanic/Latino versus not Hispanic/Latino)
- Geographic region (Asia, Latin America, Europe, North America)

## 3.8 Safety Analysis

## **3.8.1** Adverse Events

In general, if an adverse event (AE) onset is on or after the first dose of IP administration, the AE will be considered as a treatment emergent AE (TEAE). Otherwise, the AE will be considered as a non-treatment emergent AE.

An overall summary table will be showing the number and percentage of participants with at least 1 event in any of the following categories: TEAE, treatment emergent serious AE (TESAE), TEAE with outcome of death, TEAE leading to discontinuation of IP, grade 3 or higher TEAE, serious and/or grade 3 or higher TEAE, IP related TEAE, IP related TESAE.

AEs will be coded using the most recent version of MedDRA. All TEAEs will be summarized overall and by MedDRA SOC and PT, by severity and by relationship to IP. Specific AEs will be counted once for each participant for calculating rates, but all events will be presented in subject listings. In addition, if the same AE occurs multiple times within a particular participant, the highest severity and level of causality will be reported.

The TEAEs, TESAEs, TEAEs resulting in death, TEAEs leading to discontinuation of IP, Grade 3 or higher TEAEs, IP related TEAEs, and IP related TESAEs will be summarized by SOC and PT. TESAEs will be summarized by SAE criteria as well. In addition, a summary of TEAEs sorted by frequency will be presented by PT.

An AE of special interest (AESI) is an AE of scientific and medical interest specific to understanding of the IP and may require close monitoring and collection of additional information by the Investigator. AESIs for this protocol include:

- Hypersensitivity reaction, including anaphylaxis
- Viral infection/reactivation
- Opportunistic infection
- Malignancy (except non-melanoma skin cancer)

Treatment emergent AESIs will be summarized by SOC and PT.

Listings will be provided for all TEAEs and non-treatment emergent AEs.

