4 STUDY PLAN

4.1 Study Design

This study is a Phase 2, multicenter, international, double-blind, randomized, placebo-controlled, parallel-group trial to assess the efficacy and safety of VIB7734 in participants with moderate to severely active SLE.

[figure not shown]
In this study, approximately 195 participants will be randomized in a ratio of 1:1:1 (65 participants per group) to receive VIB7734 200 mg Q4W SC, VIB7734 200 mg every 12 weeks (Q12W) SC, with an additional 200 mg SC dose at Week 4, or placebo. To maintain blinding, participants randomized to the VIB7734 200 mg Q12W SC dosing regimen will receive SC placebo injections on dosing visits outside the Q12W schedule. Randomization will be stratified by SLE Disease Activity Index 2000 (SLEDAI-2K) total score at Screening (\geq 10 or < 10) and prednisone or equivalent oral GC (OGC) dose at Baseline (Day 1) (\geq 10 mg or < 10 mg).

The study will comprise a Screening period of approximately 4 weeks (Days -28 to -1), Randomization on Day 1, treatment and assessments through Week 48, and a Safety Follow-Up (SFU) period of 8 weeks (through Week 56). Under exceptional circumstances such as delayed laboratory results, drug washout, or the impact of COVID-19, the Screening period may be increased by 2 weeks, upon approval by the Medical Monitor. The study will be conducted on an outpatient basis. For all administrations, IP will be administered by site staff in the clinic and the participant will be observed for at least 60 minutes after the first and second doses. Participants who prematurely stop dosing prior to Week 44 will be followed through Week 56. Participants will not automatically be removed from the study if any administration of IP is missed.

A long-term extension (LTE) study for safety and efficacy may be offered as part of a separate protocol, to participants who complete the Week 48 visit. Participants who enter the LTE study directly after completion of the Week 48 visit will not complete the visits of the SFU period.

The study design is summarized in Figure 1.

Figure 1 Study Design

^{*}Two Week extension under exceptional consideration (delayed labs, drug wash out, COVID-19-related delays) with Medical Monitor approval.

COVID-19: coronavirus disease 2019; OGC: oral glucocorticoid; Q4W: every 4 weeks; Q12W: every 12 weeks; SC: subcutaneous(ly); SLE: systemic lupus erythematosus; SLEDAI-2K: SLE Disease Activity Index 2000; W: week.

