9.5.5 Safety Analysis

AEs will be coded using the Medical Dictionary for Regulatory Activities by System Organ Class and Preferred Term. The number and percentage of participants reporting treatment-emergent AEs with onset on or after the start of the first administration of IP will be summarized for each treatment group by System Organ Class and Preferred Term, by severity, and by relationship to the IP. The number and percentage of participants reporting treatment-emergent SAEs and treatment-emergent AESIs will also be summarized.

Clinically significant abnormalities in laboratory parameters, vital signs, ECGs, and physical examinations will be recorded as AEs or SAEs. Laboratory assessments, vital signs, and ECGs, as well as their changes from Baseline at each visit will also be summarized descriptively.

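### AE tables give only crude percentages up to each participant's last visit, so arms may be compared over unequal observation time; the effect is modest and cheap to address

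*SAP*

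**What the plan says.** SAP 3.8.1 defines a treatment-emergent event by its start alone: "if an adverse event (AE) onset is on or after the first dose of IP administration". Protocol 9.5.5 does the same, planning the "number and percentage of participants reporting treatment-emergent AEs with onset on or after the start of the first administration of IP". Neither gives an end to the window.

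The statistic is a crude proportion. The SAP overview table shows the "number and percentage of participants with at least 1 event in any of the following categories", and the tables by system organ class and preferred term follow the same logic. Rates are mentioned once: "Specific AEs will be counted once for each participant for calculating rates". That is a counting rule and supplies no time denominator.

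Collection does have an end. Protocol 8.2 stops it at the final study visit and 8.3 at exit from the study, but that date depends on the participant. Protocol 4.1 plans eight weeks of safety follow-up to Week 56, with one exception: "Participants who enter the LTE study directly after completion of the Week 48 visit will not complete the visits of the SFU period". The extension is only a possibility, under a separate protocol. For those who stop dosing early, 4.1 says: "Participants who prematurely stop dosing prior to Week 44 will be followed through Week 56". Participants who withdraw consent (6.4.3) or are lost (6.4.4) contribute less.

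Person-time appears in one place, SAP 3.5: "total participant years exposure will be summarized by treatment using the full analysis set". It is dosing time, counted to 28 days after the last dose, and no AE table uses it. SAP 4.2 takes all safety data before a calendar cut-off, without truncating at a common study week.

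**The concern.** Safety and tolerability is a stated objective, and percentages by arm will be read as comparisons even though no test is planned. A proportion with at least one event grows with the time a person is watched. Here that time depends on two things settled after randomization: entering the extension at Week 48, and leaving the study early. Both can plausibly depend on response and tolerability, so randomization does not guarantee that they balance.

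The direction cannot be predicted. More extension entry in an arm shortens its observation and lowers its percentage, and so does more study withdrawal. Part of an observed difference, or part of an apparent similarity, could therefore come from follow-up alone, and the planned tables would not let a reader separate the two.

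**Working it through.** **Follow-up length.** From Protocol 4.1, 48 + 8 = 56 weeks without the extension and 48 weeks with direct entry. The ratio is 56/48 = 1.167, so extension entry alone can create at most 8 weeks' difference. The documents state no AE risk, extension uptake or withdrawal rate; all three are assumptions below.

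**Model.** Equal constant hazard in both arms, so no true effect: λ = −ln(1 − p48)/48 and P(event by week t) = 1 − exp(−λt). An arm's crude percentage is the average of P over its members' follow-up times.

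**Extension entry only, no withdrawals.** The spurious difference is (gap in uptake) × [P(56) − P(48)].

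| 48-week risk | 56-week risk | Uptake 50% vs 70% | Uptake 40% vs 80% | Uptake 0% vs 100% |
|---|---|---|---|---|
| 5% | 5.8% | 0.2 points | 0.3 | 0.8 |
| 10% | 11.6% | 0.3 | 0.6 | 1.6 |
| 30% | 34.0% | 0.8 | 1.6 | 4.0 |
| 70% | 75.5% | 1.1 | 2.2 | 5.5 |

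Example for the 50% vs 70% column at 30% risk: 0.20 × (34.04 − 30.00) = 0.8. Mean follow-up is 0.5 × 48 + 0.5 × 56 = 52.0 weeks against 0.7 × 48 + 0.3 × 56 = 50.4 weeks, a ratio of 1.032.

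**Study withdrawal.**

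- Risk 60% by Week 48, so P(56) = 65.7% and P(24) = 36.8%. Half of those who stay enter the extension in both arms, averaging (60.0 + 65.7)/2 = 62.8%. With 10% leaving at Week 24: 0.90 × 62.8 + 0.10 × 36.8 = 60.2%. With 25% leaving: 0.75 × 62.8 + 0.25 × 36.8 = 56.3%. The gap is 3.9 points.
- Risk 30%, everyone else observed to Week 48, 10% vs 30% leaving at Week 20: 28.4% vs 25.1%, a gap of 3.2 points. The same withdrawal pattern gives 1.1 points at a 10% risk and 6.1 at a 70% risk.

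**What a Week 48 cut removes.** It removes the whole extension artefact. In the first withdrawal case it leaves 0.15 × (60.0 − 36.8) = 3.5 of the 3.9 points, because those participants left before Week 48.

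**What a person-time rate removes.** Expected time to the earlier of first event or week T is P(T)/λ. Expected events divided by expected time is therefore P(T) ÷ [P(T)/λ] = λ for any mix of follow-up times, and both artefacts vanish under this model.

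**Why the SAP 3.5 participant-years will not serve.** Duration there is last dose + 28 − first dose + 1. With doses from Day 1 to Day 309 (Week 44) this is 309 + 28 − 1 + 1 = 337 days, which leaves out the follow-up from Day 337 to Day 393. For someone whose last dose is at Day 57 but who stays to Day 393, it is 57 + 28 − 1 + 1 = 85 days, although events count over all 393.

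**The case against.** The strongest reply is that the effect is small and hypothetical. At a 60% risk, uptake of 80% vs 50% moves the percentages to 61.1% vs 62.8%. That is 1.7 points, or about 1.1 of 65 participants. The 90% half-width on such a difference is about 1.645 × √[(0.611 × 0.389 + 0.628 × 0.372)/65] = 14 points. The extension may not be offered, and balanced uptake gives no artefact. Participants who stop dosing are meant to remain under observation, so high discontinuation of investigational product does not by itself shorten AE follow-up. Safety output is descriptive. Disposition with reasons, a Kaplan-Meier plot of product discontinuation and full AE listings are planned. All of this stands and limits the size of the point. However, those outputs only help a reader notice unequal withdrawal; none adjusts for it.

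Several stronger readings are tempting, and the documents do not support them:

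- A reader might infer that events are counted indefinitely. They are not: Protocol 8.2 and 8.3 bound collection, though at a date that varies by participant.
- A reader might take the rise from 5.0% to 5.8% (16% relative) as a likely AESI difference between arms. It is one only at 0% vs 100% uptake. At 80% vs 50% the figures are 5.16% and 5.40%, or 0.24 points.
- A reader might make much of exposure being summarized on the full analysis set and AEs on the safety set. Both sets require a dose, so the groupings differ only if someone received a treatment other than the one assigned.
- A reader might conclude that the main AE tables should stop at Week 48. That would move late events, including rare AESIs, out of the comparison that the follow-up period exists to inform.

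**Conclusion.** The point holds as a minor reporting gap. SAP 3.8.1 plans crude percentages over participant-specific observation periods and no summary that allows for this. Whether the arms actually differ in observation time is unknown; it depends on extension entry or study withdrawal differing by arm.

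Under a constant and equal hazard, the artefact is about 0.2 to 2 points for assumed 20- to 40-point gaps in extension entry. For assumed 15- to 20-point gaps in withdrawal around Weeks 20 to 24 it is about 3 to 4 points at 48-week risks of 30% to 60%, smaller for rarer events and larger for commoner ones. Early withdrawal is potentially the larger source. Nothing here shows that the safety comparison will be misleading.

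One loose end affects the denominators. For participants who stop product early, Protocol 4.1 gives follow-up through Week 56, while 6.4.3 gives visits through Week 48/ET and at least 12 weeks after the last dose. These passages must be reconciled.

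**What to change.** In SAP 3.8.1, keep the planned tables and add two things.

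1. For any TEAE, any serious TEAE and each AESI category: incidence per 100 participant-years of observation, counting time from first dose to the earlier of first event or last study contact. Use the safety analysis set by treatment received, and state that the SAP 3.5 dosing-time participant-years are not the denominator.
2. One overall summary limited to events with onset up to the Week 48 visit, with later events shown separately.

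Say what each is for: the Week 48 summary removes only the extension artefact, and the person-time rate is what addresses early withdrawal.

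The cost is SAP wording and a few tables from data already collected, with no change to conduct or sample size. The limitation to state is that the rate assumes a roughly constant hazard, which is doubtful for hypersensitivity reactions, and pools time on and off treatment.
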